7.1.14. JC Virus (JCV) Monitoring and Progressive Multifocal Leukoencephalopathy (PML)

PML is an opportunistic infection of the brain caused by the JC virus (JCV) in immunosuppressed subjects, and has been observed in subjects receiving B-cell depleting agents, including rituximab, as well as with other immunosuppressive agents. Investigators should consider a diagnosis of PML in subjects who present with new-onset neurological manifestations, such as gait disturbances, memory loss, cognitive disorders, or visual

symptoms, and a neurology consult, brain MRI and lumbar puncture should be considered. There is no currently accepted screening test for PML. The disease course of PML is usually progressive and fatal. To monitor for the potential of PML, samples for JCV testing will be collected according to [Schedule of Activities](#).

Reductions or discontinuation of concomitant immunosuppressive therapy and appropriate treatment including antiviral therapy should be considered. There are no known interventions that can reliably prevent PML or adequately treat PML if it occurs. The majority of patients who develop PML have a fatal outcome.

Any suspected case of PML should be reported as an SAE. If a confirmed or probable case of PML is observed in this or other ongoing PF-06835375 studies, the sponsor will hold dosing for all subjects until the benefit risk assessment of PF-06835375 is re-evaluated by the sponsor.

7.1.15. Viral Surveillance

Blood samples for possible analysis of cytomegalovirus (CMV), Epstein-Barr virus (EBV), herpes simplex virus type 1 & 2 (HSV-1, HSV-2) and varicella-zoster virus (VZV) will be collected according to the times outlined in the [Schedule of Activities](#). Details regarding the collection, processing, storage and shipping of the blood samples will be provided in the lab manual.

Note: Due to delayed reporting times for these assays, the results might not be available along with the other study tests.

In addition to time points specified, a blood sample for viral surveillance sample may also be taken at the time of an AE, as clinically appropriate.

7.1.16. Suspected Herpetiform Rash

For any occurrence of a suspected herpetiform rash (eg, herpes simplex and herpes zoster), specimens for viral DNA analysis will be obtained: A swab of the affected area will be collected for confirmation; a blood sample for viral surveillance will be collected for the analysis of viral load. Details for these collections will be provided in the laboratory manual.

7.1.17. Assessment of Suicidal Ideation and Behavior

The Columbia Suicide Severity Rating Scale (C-SSRS) is an interview based rating scale to systematically assess suicidal ideation and suicidal behavior.¹⁹ Versions are available for “Lifetime” and “Since Last Visit”. The “Lifetime” evaluation is done at screening, and “Since Last Visit” is done at all other time points.

The C-SSRS should be collected at times specified in the [Schedule of Activities](#) section of this protocol by an appropriately trained clinical site staff member. The C-SSRS can also be administered at any time in the study at the discretion of the investigator based on any reasonable concern.

At each suicidality assessment as per [Schedule of Activities](#), subjects felt to have significant suicidal ideation with actual plan and intent or suicidal behavior, must be evaluated by a clinician/mental health professional (MHP) skilled in the evaluation of suicidality in the subjects by virtue of training or experience (eg, psychiatrist, licensed clinical psychologist) who will determine if it is safe for the subject to participate/continue in the trial. Specific criteria that indicate a need for such an assessment are:

- Suicidal ideation associated with actual intent and/or plan in the past year; (a “YES” answer to C-SSRS questions 4 “some intent to act without specific plan” or 5 “specific plan and intent”).
- Previous history of suicide behaviors in the past 10 years (a “YES” answer to any of the suicidal behavior items of the C-SSRS with the behavior occurring in the past 10 years).
- The presence of any current major psychiatric disorder that is not explicitly permitted in the inclusion/exclusion criteria and in the investigator’s judgment would interfere with study participation.
- Any lifetime history of serious or recurrent suicidal behavior. [Non-suicidal self-injurious behavior is not a trigger for a risk assessment unless in the investigator’s judgment it is indicated].
- In the investigator’s judgment a risk assessment or exclusion is warranted.

A written copy of the risk assessment should be included in the subject’s source documentation.

Other possible suicidality adverse events or other clinical observations may, based on the judgment of the investigator, also trigger a risk assessment and require a narrative.

Suicidality adverse events or other clinical observations may, based on the judgment of the investigator and clinician/MHP, also trigger a risk assessment and a narrative using information from the C-SSRS, and available information, prior to screening and baseline information, and the clinician/MHP assessment. When there is a positive response to any question on the C-SSRS, the investigator should determine whether an adverse event has occurred.

7.2. Pharmacokinetics

7.2.1. Serum for Analysis of PF-06835375

During all study periods, blood samples for PK analysis will be collected at times specified in the [Schedule of Activities](#). A serum separator tube should not be used.

The actual times may change but the number of samples will remain the same. All efforts will be made to obtain the PK samples at the exact nominal time relative to dosing. However, samples obtained within 10% of the nominal time (eg, within 6 minutes of a

60 minute sample) from dosing will not be captured as a protocol deviation, as long as the exact time of the sample collection is noted on the source document and data collection tool (CRF).

- Samples will be analyzed using a validated analytical method in compliance with Pfizer standard operating procedures. Placebo PK samples will not be analyzed.
- Details regarding the collection, processing, storage and shipping of the blood samples will be provided in the lab manual.
- The PK samples must be processed and shipped as indicated to maintain sample integrity. Any deviations from the PK processing steps, including any actions taken, must be documented and reported to the sponsor. On a case-by-case basis, the sponsor may make a determination as to whether sample integrity has been compromised. Any sample deemed outside of established stability, or of questionable integrity, will be considered a protocol deviation.

C
C
I

7.2.2. Shipment of Pharmacokinetic Samples

The shipment address and assay lab contact information will be provided to the investigator site prior to initiation of the study.

7.3. Immunogenicity

7.3.1. Serum for Analysis of Anti-PF-06835375 Antibodies and Neutralizing Anti-PF-06835375 Antibodies

Blood samples for the detection of Anti-PF-06835375 Antibodies (ADA) and Neutralizing Anti-PF-06835375 Antibodies (NAb) will be collected at the times specified in the [Schedule of Activities](#).

[figure not shown]
Details regarding the collection, processing, storage and shipping of the blood samples will be provided in the lab manual.

7.3.2. Immunogenicity Analyses

The immunogenicity samples must be processed and shipped as indicated to maintain sample integrity. Any deviations from the immunogenicity processing steps, including any actions taken, must be documented and reported to the sponsor. On a case-by-case basis, the sponsor may make a determination as to whether sample integrity has been compromised. Any sample deemed outside of established stability, or of questionable integrity, will be considered a protocol deviation.

Samples will be analyzed using validated analytical methods in compliance with sponsor standard operating procedures. Samples tested as ADA positive, (not just confirmed positive, but also with a titer positive result) will be further tested for NAb using validated NAb assays.

Samples collected for detecting ADA and NAb will be retained in accordance to local regulations and if not used within this timeframe, will be destroyed. **CC1**

[figure not shown]
7.3.3. Shipment of Immunogenicity (ADA/NAb) Samples

The shipment address and assay lab contact information will be provided to the investigator site prior to initiation of the study.

CC1

[figure not shown]

CC1

DNA; however, the biospecimen may also be used to study other molecules (eg, RNA, proteins, and metabolites).

CCI

7.5. Rater Qualifications

For specific rating assessments, only qualified raters will be allowed to evaluate and/or rate subjects in this study. The minimum qualifications a rater must meet for each study rating assessment will be outlined in the Rater Assessment Manual provided to each participating site. The level of experience with the target population (or equivalent), specific scale experience (or equivalent), and certification required (if applicable) will be listed and used to

determine whether a rater is approved for a given assessment. Proposed raters who do not meet specific criteria but who may be qualified based on unique circumstances may be individually reviewed by the study clinical team to determine whether or not a waiver may be issued. The rater must become certified to perform selected study assessments before he or she can participate in the conduct of the study. For specifically defined assessments, rater training and standardization exercises may be conducted, and written and signed documentation will be provided by the site for each rater's certification. In return, each site will be provided written and signed documentation outlining each rater's certification for specific study assessments. Recertification may be required at periodic intervals during the study. The raters who administer specific study assessments will be documented in a centralized location and all site staff who administer ratings will be verified in the site study documentation during the conduct of the study.

7.6. Pharmacodynamics CCI

Blood samples for pharmacodynamics (PD) will be collected according to the [Schedule of Activities](#). Details regarding the collection, processing, storage and shipping of the blood samples will be provided in the lab manual.

The PD samples must be processed and shipped as indicated to maintain sample integrity. Any deviations from the PD processing steps, including any actions taken, must be documented and reported to the sponsor. On a case-by-case basis, the sponsor may make a determination as to whether sample integrity has been compromised. Any sample deemed outside of established stability or of questionable integrity will be considered a protocol deviation.

CCI

7.6.1. Samples Collected for All Subjects (both RA and SLE)

The following samples will be collected for all subjects

CCI

CCI

[REDACTED]

[REDACTED]

CCI

[REDACTED]

[REDACTED]

[REDACTED]

[REDACTED]

[REDACTED]

[REDACTED]

[REDACTED]

CCI

[REDACTED]

[REDACTED]

7.6.1.5. Erythrocyte Sedimentation Rate (ESR)

Blood samples for analysis of ESR will be collected at the visits specified in the [Schedule of Activities](#). The ESR will be done locally.

7.6.1.6. B-cell Activating Factor (BAFF)

Blood samples for the analysis of B-cell activating factor (BAFF) will be collected according to times outlined in the [Schedule of Activities](#). BAFF is also known as B Lymphocyte Stimulator (BLyS).

CCI

[REDACTED]

[REDACTED]

CCI

[REDACTED]

CCI

CCI

7.6.3. Samples Collected for Subjects with SLE

The following samples will be collected for subjects with SLE. In case a subject has diagnoses of both RA and SLE, both RA and SLE samples will be collected.

7.6.3.1. Anti-nuclear Antibodies

Blood samples will be collected for Anti-nuclear Antibodies (ANA), according to the times outlined in the [Schedule of Activities](#).

CCI

CCI

CCI

CCI

7.7. Blood Volume

The total blood sampling volume for individual subjects in this study is as follows.

In Part A, during the first 16 weeks, the total blood volume will be approximately 820 mL. If subjects remain in the study in Part A beyond Week 16, the total blood volume every 12 weeks will be approximately 250 ml.

In Part B, during the first 16 weeks, the total blood volume will be approximately 900 mL. If subjects remain in the study in Part B beyond Week 16, the total blood volume every 12 weeks will be approximately 250 ml.

Additional blood samples may be taken for safety assessments or to repeat screening assessments (if appropriate) as described in the [Schedule of Activities](#), provided the total volume taken during the study does not exceed 550 mL during any period of 30 consecutive days.

7.8. Diagnostic and Efficacy Assessments

7.8.1. American College of Rheumatology/European League Against Rheumatism Classification for RA

[figure not shown]
Eligibility for the study for subjects with RA will be evaluated according to the 2010 American College of Rheumatology (ACR)/European League Against Rheumatism (EULAR) Classification Criteria for Rheumatoid Arthritis (See [Appendix 6](#)).²¹ Subjects are required to have a score of 6 or greater at Screening, with symptom duration at least 6 months prior to Screening visit.

7.8.2. American College of Rheumatology/SLICC Criteria for the Classification of SLE

[figure not shown]
Eligibility for the study for subjects with SLE will be evaluated according to the American College of Rheumatology (ACR) / SLICC Criteria for the Classification of SLE (See [Appendix 5](#)).²² These criteria require that subjects satisfy 4 of the clinical and immunologic criteria used in the SLICC classification criteria, including at least 1 clinical criterion and 1 immunologic criterion, OR that subject has biopsy-proven nephritis compatible with SLE in the presence of ANAs or anti-dsDNA antibodies.

In addition, subjects are also required to have symptoms at least 6 months prior to Screening visit.

CCI

CCI

CCI

CCI

|| 

|| 

[figure not shown]
[figure not shown]
|| 

|| 

[figure not shown]
CCI

CCI

[figure not shown]
CCI

[figure not shown]
[figure not shown]

CCI

CCI

CCI

7.8.4.2. Patient's Global Assessment (PtGA) of Arthritis

This will be collected only for RA subjects. Subject will answer the following question, “Considering all the ways your arthritis affects you, how are you feeling today?” The subject’s response will be recorded using a 100 mm visual analog scale (VAS) (See [Appendix 10](#)). This assessment must be performed early in the clinic visit and before the subject has extensive contact with site personnel and/or investigator and prior to dosing.

8. ADVERSE EVENT REPORTING

8.1. Requirements

The table below summarizes the requirements for recording safety events on the CRF and for reporting safety events on the Clinical Trial (CT) Serious Adverse Event (SAE) Report Form to Pfizer Safety. These requirements are delineated for 3 types of events: (1) SAEs; (2) non-serious adverse events (AEs); and (3) exposure to the investigational product under study during pregnancy or breastfeeding, and occupational exposure.

Safety Event	Recorded on the CRF	Reported on the CT SAE Report Form to Pfizer Safety Within 24 Hours of Awareness
SAE	All	All
Non-serious AE	All	None
Exposure to the investigational product under study during pregnancy or breastfeeding, and occupational exposure	All (regardless of whether associated with an AE), except occupational exposure	Exposure during pregnancy, exposure via breastfeeding, occupational exposure (regardless of whether associated with an AE)

All observed or volunteered events regardless of treatment group or suspected causal relationship to the investigational product(s) will be reported as described in the following paragraphs.

Events listed in the table above that require reporting to Pfizer Safety on the CT SAE Report Form within 24 hours of awareness of the event by the investigator **are to be reported regardless of whether the event is determined by the investigator to be related to an investigational product under study**. In particular, if the SAE is fatal or life-threatening, notification to Pfizer Safety must be made immediately, irrespective of the extent of available event information. This time frame also applies to additional new (follow-up) information on previously forwarded reports. In the rare situation that the investigator does not become immediately aware of the occurrence of an event, the investigator must report the event

within 24 hours after learning of it and document the time of his/her first awareness of the event.

For each event, the investigator must pursue and obtain adequate information both to determine the outcome and to assess whether it meets the criteria for classification as an SAE (see the [Serious Adverse Events](#) section below). In addition, the investigator may be requested by Pfizer Safety to obtain specific follow-up information in an expedited fashion. This information is more detailed than that recorded on the CRF. In general, this will include a description of the event in sufficient detail to allow for a complete medical assessment of the case and independent determination of possible causality. Any information relevant to the event, such as concomitant medications and illnesses, must be provided. In the case of a subject death, a summary of available autopsy findings must be submitted as soon as possible to Pfizer Safety. Any pertinent additional information must be reported on the CT SAE Report Form; additional source documents (eg, medical records, CRF, laboratory data) are to be sent to Pfizer Safety **ONLY** upon request.

As part of ongoing safety reviews conducted by the sponsor, any non-serious AE that is determined by the sponsor to be serious will be reported by the sponsor as an SAE. To assist in the determination of case seriousness, further information may be requested from the investigator to provide clarity and understanding of the event in the context of the clinical study.

8.1.1. Additional Details On Recording Adverse Events on the CRF

All events detailed in the table above will be recorded on the AE page(s) of the CRF. It should be noted that the CT SAE Report Form for reporting of SAE information is not the same as the AE page of the CRF. When the same data are collected, the forms must be completed in a consistent manner. AEs should be recorded using concise medical terminology and the same AE term should be used on both the CRF and the CT SAE Report Form for reporting of SAE information.

8.1.2. Eliciting Adverse Event Information

The investigator is to record on the CRF all directly observed AEs and all AEs spontaneously reported by the study subject. In addition, each study subject will be questioned about the occurrence of AEs in a non-leading manner.

8.1.3. Withdrawal From the Study Due to Adverse Events (see also the [Subject Withdrawal](#) section)

Withdrawal due to AEs should be distinguished from withdrawal due to other causes, according to the definition of AE noted below, and recorded on the CRF.

When a subject withdraws from the study because of an SAE, the SAE must be recorded on the CRF and reported, as appropriate, on the CT SAE Report Form, in accordance with the [Requirements](#) section above.

8.1.4. Time Period for Collecting AE/SAE Information

The time period for actively eliciting and collecting AEs and SAEs (“active collection period”) for each subject begins from the time the subject provides informed consent, which is obtained before the subject’s participation in the study (ie, before undergoing any study-related procedure and/or receiving investigational product), through and including and including a minimum of 90 calendar days after the last administration of the investigational product. For subjects who are in the study beyond 90 calendar days after the last administration of the investigational product (expected for most subjects), the end of study visit will be used as a minimum cut-off.

For subjects who are screen failures, the active collection period ends when screen failure status is determined.

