Administration of PF-06835375 or placebo ^{bb}			X						X												
CCI																					
Monitoring																					
Contraception check	X	X		X	→	→	→	X		X	→	→	→	→	→	→	→	→	→	→	X
Serious and non-serious adverse event monitoring	X	→	→	→	→	→	→	→	→	→	→	→	→	→	→	→	→	→	→	→	X
Concomitant treatment(s)		X	→	→	→	→	→	→	→	→	→	→	→	→	→	→	→	→	→	→	X
TB monitoring ^{dd}		X		X	→	→	→	X		X	→	→	→	→	→	→	→	→	→	→	X
Infections monitoring ^{ee}	X	X	→	→	→	→	→	→	→	→	→	→	→	→	→	→	→	→	→	→	X
Infusion/Injection Site Reactions ^{ff}			X	→	→	X			X	→	X										

Abbreviations: →= ongoing/continuous event; ACR/EULAR = American College of Rheumatology/European League Against Rheumatism; CCI [REDACTED]
BAFF = B-cell activating factor; CCI [REDACTED] C-SSRS = Columbia-Suicide Severity Rating Scale; CRU = clinical
research unit; ECG = electrocardiogram; ESR = erythrocyte sedimentation rate; FSH = follicle-stimulating hormone; HIV = human immunodeficiency virus;
CCI [REDACTED] Ig = Immunoglobulin; IGRA = Interferon gamma release assay; JCV = JC virus; PK = Pharmacokinetic; RA = rheumatoid arthritis;
SLE = systemic lupus erythematosus; CCI [REDACTED] SLICC= Systemic Lupus International Collaborating Clinics;
TB = tuberculosis.

- a. Day relative to start of study treatment (Day 1).
- b. Prior to admission to the research unit, review changes in the subject's medical history, concomitant medications and medical procedures since the Screening visit, perform contraception check and confirm that there are no changes to subject's eligibility. If a subject has any clinically significant, study related abnormalities at the conclusion of a scheduled inpatient portion of the study on Day 2 or at the end of the outpatient visit on Day 29, it is at the investigator's discretion to ask the subject to remain in the clinical unit until it is safe for outpatient follow up. The investigator must promptly notify the sponsor clinician or medical monitor. If the subject is unable or unwilling to remain in the clinical unit, the investigator should make every effort to arrange follow up evaluations at appropriate intervals. All Day 2 assessments should be completed prior to discharge from the research unit.
- c. Day 30 phone visit to occur one day after administration of IP on Day 29. It is at investigator's discretion to conduct an in clinic visit instead of a phone visit.

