1.6. Summary of Benefits and Risks

Based on the available nonclinical data, the risks and potential benefits for PF-06835375 are considered to be favorable and support clinical development in subjects with SLE and RA.

SLE and RA both have higher prevalence in females and hence the trial objectives cannot be met without inclusion of women of childbearing potential (WoCBP). Nonclinical data to date (Section 1.2.6) have not identified any risk to reproductive organs in sexually mature cynomolgus monkeys, the pharmacologically relevant species. Given that an enhanced pre- and postnatal development study (ePPND) will be conducted later in development, this protocol that allows enrollment of WoCBP has stringent requirements to mitigate unintended exposures (pregnancy testing and use of contraceptives; see Section 4.4.1). Subjects will be followed for a minimum of 16 weeks after Day 1 during the study, which extends beyond predicted drug exposure of five half-lives based on expected PK.

Based on studies with other B cell and T cell depleting agents, there is a dose-dependent risk for infusion and injection reactions with PF-06835375, potentially severe. Subjects will be closely monitored for 8-12 hours post-infusion as per Schedule of Activities. As described in Section 5, subjects will be pre-medicated to mitigate this risk, and peri- and post-infusion medications to manage infusion and/or injection reactions will be available for subjects receiving IP.

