3. STUDY DESIGN

3.1. Study Overview

This is a Phase 1, randomized, multi-center, double-blind, sponsor open, placebo-controlled, single and multiple dose-escalation study to evaluate the safety, tolerability, pharmacokinetics, and pharmacodynamics of PF-06835375 in subjects with seropositive SLE or RA. Both IV and SC routes of administration will be tested.

This study will include two parts: Part A, consisting of approximately eight single ascending dose (SAD) cohorts, and Part B, consisting of approximately 6 multiple ascending dose (MAD) cohorts. Fewer cohorts may be included in each part at Sponsor's discretion. Cohorts in Part A will be initiated sequentially. Subjects in Part B will receive two doses of investigational product (first dose on Day 1 and second dose on Day 29), and will be enrolled concurrently with Part A following the completion of the initial cohorts in Part A (See [Section 3.3](#)). Subjects who are randomized in Part A will not be eligible to participate in Part B of this study.

[figure not shown]
This study will enroll up to a total of approximately 112 subjects at approximately 10 sites.

The study includes a Screening visit to assess eligibility and subsequent visits for a minimum of 16 weeks. Subjects who meet the end of study criteria (See [Section 3.5](#)) will have one follow-up phone call visit which will represent the end of study visit. Subjects, who do not meet the criteria to leave the study at Week 16, will continue with clinic visits every four weeks until Week 52 and then every 12 weeks until they meet these criteria. Overall, subjects are expected to stay in the study approximately 6-12 months (including screening). Subjects who withdraw from the study may be replaced at the discretion of the sponsor. A replacement subject will receive the same treatment as the withdrawn subject.

Both SLE and RA subjects will be enrolled into this study. Minimum disease activity (ie, [CCI](#) [REDACTED] or DAS28 cutoffs) is not required for entry as inclusion criteria. All subjects in both Part A and B will be followed for a minimum of 16 weeks prior to being able to qualify for study completion based on the cellular recovery (See [Section 3.5](#)).

It is at the sponsor's discretion to dose escalate (See [Section 3.4.1](#)), to repeat the same dose, or to test a lower dose based on emerging data.

[CCI](#)

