3.5. Criteria for End of Study

All subjects will be followed through the Week 16 visit. In order for the Week 16 visit to be the subject's last clinic study visit, B cell counts meet at least one of these criteria:

- B cell count is \geq 50% of baseline value AND is stable or increasing between Week 12 and Week 16 measurements, OR
- B cell count is \geq lower limits of normal (defined as 80 cells/ μ l¹⁹) at Week 16.

If at least one of the above criteria are not met at Week 16, subjects will continue in the study and will be followed until B cell count meets at least one of these criteria:

- B cell count is \geq 50% of baseline value AND is stable or increasing between the two measurements at least two weeks apart, OR
- B cell count is \geq lower limits of normal (defined as 80 cells/ μ l¹⁹), OR
- B cell count reaches a new stable (or increasing) detectable level AND subject is clinically stable for minimum of two consecutive visits, each at least two weeks apart, based on the assessment by both the sponsor AND the investigator. The earliest B cell count that can be considered for this criterion is from the Week 20 visit. As a result, subjects will not be discharged prior to availability of Week 24 lab results for B cells under this criterion.

B-cell counts obtained from CLIA certified central lab will be used for this determination.

Baseline value is defined as the average of Screening and Day 1 pre-dose values. In cases where only one value (ie, screening or Day 1 pre-dose) is available, this one value will be used as the baseline. Stable is defined as ± 5 cell/ μ l. Values obtained by the central lab will be used.

B cell counts data will be available only after subject completes the clinic visit due to the required shipment of samples to central lab and their processing time. Once subject meets the criteria for the end of study described above, a phone visit will take place within approximately 1-2 weeks, prior to the next scheduled in clinic visit. This phone visit will be considered the end of study visit/last visit.

Subjects may be asked to return for additional follow up visits beyond the anticipated end of study visit for safety reasons as determined by the Investigator in consultation with the sponsor medical monitor.

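### In Part B the end-of-study call can fall as early as 81 days after dose 2, short of the protocol's 90-day minimum for adverse-event collection, because the schedule counts from Day 1

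*Protocol*

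**What the plan says.** Protocol Section 8.1.4 runs active collection of adverse events and serious adverse events, for each subject, from consent through "a minimum of 90 calendar days after the last administration of the investigational product". For subjects still in the study after that point, which is "expected for most subjects", it says that "the end of study visit will be used as a minimum cut-off". That second rule is limited to subjects who have passed 90 days. It does not replace the minimum for anyone else.

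Follow-up is timed from a different origin. In Part B, subjects receive "two doses of investigational product (first dose on Day 1 and second dose on Day 29"), and the Part B Schedule of Activities defines its visit days as "Day relative to start of study treatment (Day 1"). Section 1.6 states the follow-up floor in the same way: subjects are "followed for a minimum of 16 weeks after Day 1 during the study". The schedule allows dose 2 on Day 26-32 and the Week 16 visit on Day 106-120.

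Under Section 3.5, once a subject's B-cell count meets a discharge criterion, "a phone visit will take place within approximately 1-2 weeks, prior to the next scheduled in clinic visit". It adds: "This phone visit will be considered the end of study visit/last visit". In the schedule, adverse-event monitoring ends at that call. Further visits are possible only for safety reasons, as determined by the investigator in consultation with the sponsor's medical monitor.

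**The concern.** Section 8.1.4 counts from the last dose, whereas the schedule and the discharge rule count from Day 1. In Part A these are the same day. In Part B they are about four weeks apart, and nothing in Section 3.5 ties the final call to the date of dose 2. A site could keep every visit inside its window, discharge a subject at Week 16 as Section 3.5 directs, and make the last scheduled contact before 90 days have passed since dose 2.

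At stake is whether the schedule delivers a safety-collection minimum that the protocol sets for itself. Treatment-emergent events and infections are primary endpoints (Protocol Section 2), and planned contacts are how such events are actively elicited.

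**Working it through.** **Inputs**
- Minimum collection period: 90 days after the last dose (Protocol 8.1.4).
- Dose 2: Day 29 ± 3, that is Day 26-32 (Part B Schedule of Activities).
- Week 16 visit: Day 113 ± 7, that is Day 106-120 (same schedule).
- Lag from visit to call: 7-14 days. This is an assumption. Section 3.5 gives about 1-2 weeks once the criterion is met and does not say whether the clock starts at the visit or at the laboratory result.

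**Formula**

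Days from dose 2 to call = (Week 16 study day + lag) − dose 2 study day.

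**Nominal schedule and window limits**

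| Dose 2 | Week 16 | Dose 2 to Week 16 (days) | Call at lag 7 | Call at lag 14 |
|---|---|---|---|---|
| Day 29 | Day 113 | 84 | 91 | 98 |
| Day 29 | Day 106 | 77 | 84 | 91 |
| Day 32 | Day 113 | 81 | 88 | 95 |
| Day 32 | Day 106 | 74 | 81 | 88 |
| Day 26 | Day 120 | 94 | 101 | 108 |

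The nominal schedule meets the minimum with 1-8 days to spare. The in-window range is 81 to 108 days, so the largest shortfall is 90 − 81 = 9 days. A late dose 2 is enough on its own: Day 32 with Week 16 exactly on Day 113 and a 7-day lag gives 88 days.

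**Dependence on the lag**

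There are 7 × 15 = 105 pairs of in-window dates for dose 2 and Week 16. The number that give a call before 90 days is:
- lag 7 days: 42 of 105 (40%)
- lag 10 days: 21 of 105 (20%)
- lag 14 days: 3 of 105 (3%)
- lag 15 days: 1 of 105 (only Day 32 with Day 106, 74 + 15 = 89)
- lag 16 days: none (74 + 16 = 90)

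Over all lags from 7 to 14 days, 160 of 105 × 8 = 840 combinations (19%) fall short. These figures count calendar combinations. They are not predicted frequencies, because the documents give no distribution of visit or call dates.

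**Who is outside the problem**
- Part A: the only dose is on Day 1, so the earliest Week 16 visit is already 106 − 1 = 105 days after it.
- Part B subjects who do not receive dose 2: their last dose is also on Day 1.
- Subjects kept beyond Week 16: Week 20 is nominally Day 20 × 7 + 1 = 141. Even 14 days early (Day 127) with dose 2 on Day 32, that is 95 days.

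**When the minimum is reached**

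Ninety days after dose 2 is study Day 116, 119 or 122 for dose 2 on Day 26, 29 or 32. All of these precede the Week 20 visit, so a call that satisfies Section 8.1.4 can still be made before the next clinic visit, as Section 3.5 asks.

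**The case against.** The strongest reply is that the two sections can both be obeyed. Section 8.1.4 already binds for each subject, and an early call does not cancel it. Its wording foresees that not everyone will be in the study past 90 days. A call at 14 days satisfies the rule in 102 of 105 date pairs, and the other three need 15 or 16 days, which an approximate interval of 1-2 weeks can accommodate. Section 3.5 also notes that B-cell results come only after shipment and central processing, so the clock may well start at the result, which pushes the call later. On this view all that is missing is a cross-reference.

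Much of that stands. It does not close the gap: after an early call nothing is scheduled through which the remaining days could be covered, and nothing in Section 3.5 prompts a site to wait.

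Three stronger readings are tempting, and the documents do not support them.
- **That about a fifth of Week 16 discharges would fall short.** The 19% holds only if every in-window combination is equally likely, for which there is no basis.
- **That the shortfall falls mainly on placebo and low-dose subjects.** For placebo, early discharge is a reasonable inference: entry requires at least 80 cells/µL (Protocol 4.2) and 80 cells/µL at Week 16 is sufficient for release. For low doses it cannot be quantified. No human recovery times by dose are given, and Part B is expected to start only after counts in Part A have fallen to about 10 cells/µL (Protocol 3.3). The visit windows themselves do not depend on treatment.
- **That this shortfall explains unequal safety follow-up between arms.** That inequality comes from the B-cell discharge rule, which can hold depleted subjects to Week 52 and beyond. It is a separate matter, and moving a call by a few days leaves it essentially as it was. Neither the primary endpoints nor the visible SAP text uses a 90-day window; SAP Section 6.2.1 counts follow-up events as treatment emergent.

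**Conclusion.** The point holds as a minor mismatch between sections, confined to Part B subjects who receive dose 2 and are discharged at Week 16. As written, the schedule does not guarantee the 90-day minimum. With the call counted 7-14 days from the Week 16 visit, the nominal schedule complies at 91-98 days, but a fully in-window subject can have the last contact at 81-89 days.

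The result rests on where the 1-2 weeks start. If they run from the laboratory result, the shortfall shrinks, and it is gone once the call is at least 16 days after the visit. If calls under 7 days are allowed, the earliest contact could come before 81 days. The number of subjects affected cannot be estimated from the documents, but the scale is small: cohorts B1-B5 plan 10 placebo subjects in total (5 × 2), and SAP Section 2.1 records that optional cohort X6 was not used. Nothing here shows that a conclusion of the trial would change.

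**What to change.** Reconcile Section 3.5 and the end-of-study note to the Part B schedule with Section 8.1.4 by stating that the end-of-study call is made no earlier than 90 days after the subject's actual last dose. The same sentence should say whether the 1-2 weeks run from the clinic visit or from receipt of the B-cell result.

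The cost is one sentence. With a 7-14 day lag from the visit, some calls move later by at most about 9 days (the extreme case from Day 113 to Day 122, 16 days after the visit). No clinic visit or blood sample is added.

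SAP Section 2.1 already reports the doses actually given, so some calls may have been made. For those, list the Part B subjects whose last contact came before 90 days after the last dose, with the number of days by treatment group, and note it beside the adverse-event summaries. This uses dates already recorded.
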